6.2.11.2 PK Parameters and Methodology

Concentration-time data for donepezil and active metabolite 6-O-desmethyl donepezil and will be analyzed using noncompartmental methods in PhoenixTM WinNonlin[®] (Version 8.1 or higher, Certara, L.P.) in conjunction with the internet-accessible implementation of Pharsight[®] Knowledgebase ServerTM (PKSO; Version 4.0.4, Certara, L.P.). PKSO provides protected and structured storage, audit trails, and version control for clinical study data, analyses, and related files, supporting Food and Drug Administration (FDA) 21 CFR Part 11 compliance. The PK population will be used to calculate PK parameters.

In the PK analysis, BLQ concentrations will be treated as zero from time-zero up to the time at which the first quantifiable concentration is observed; embedded and/or terminal BLQ

Page 16 of 61 Confidential

concentrations will be treated as "missing". Actual time relative to TDS #5 application (Days 29 through 35) will be used in the PK analysis. If actual time is missing, nominal (scheduled) time will be used. Actual predose sample times will be set to zero prior to PK analysis.

The following PK parameters will be calculated for Weeks 1 and 5 for donepezil and 6-O-desmethyl donepezil for TDS:

WORLDWIDE CLINICAL TRIALS SCIENTIFICALLY MINDED • MEDICALLY DRIVEN Corium, Inc. CL-P-20003 Statistical Analysis Plan Version 2.0 Issue Date 15-JUL-2021

Parameter	Description			
Week 1 (Single Dos	e)			
AUC ₀₋₂₄	The area under the plasma concentration versus time curve, from time zero to 24 h post TDS #1 application, calculated by the linear trapezoidal rule for 24 h intervals within Week 1 (i.e., there will be a total of 7 values for AUC ₀₋₂₄ for Day 1 to Day 7 in Week 1)			
	These will be calculated using the partial area function in WinNonlin (ie, AUC ₀₋₂₄ , AUC ₂₄₋₄₈ , AUC ₄₈₋₇₂ , AUC ₇₂₋₉₆ , AUC ₉₆₋₁₂₀ , AUC ₁₂₀₋₁₄₄ , and AUC ₁₄₄₋₁₆₈)			
AUC ₀₋₁₆₈	The area under the plasma concentration versus time curve during a 1 week period (AUC during the wear period for Week 1), calculated by the linear trapezoidal rule.			
C _{max}	The maximum observed plasma concentration over a dosage interval following the first TDS application (Week 1)			
T _{max} ,	Time to reach C_{max} after first TDS application on Week 1. If the maximum value occurs at more than one time point, T_{max} is defined as the first time point with this value.			
T _{lag}	Lag time: time for the drug to appear in the systemic circulation after the first TDS application on Week 1			
Week 5 (Steady-Sta	te)			
AUC ₀₋₂₄	The area under the plasma concentration versus time curve, from time zero to 24 h post TDS #5 application, calculated by the linear trapezoidal rule for 24 h intervals within Week 5 (i.e., there will be a total of 7 values for AUC ₀₋₂₄ for Day 1 to Day 7 in Week 5).			
	(ie, AUC ₀₋₂₄ , AUC ₂₄₋₄₈ , AUC ₄₈₋₇₂ , AUC ₇₂₋₉₆ , AUC ₉₆₋₁₂₀ , AUC ₁₂₀₋₁₄₄ , and AUC ₁₄₄₋₁₆₈)			

Page 18 of 61 Confidential

WORLDWIDE CLINICAL TRIALS SCIENTIFICALLY MINDED • MEDICALLY DRIVEN Corium, Inc. CL-P-20003 Statistical Analysis Plan Version 2.0 Issue Date 15-JUL-2021

AUC _{0-168,ss} (AUC _{tau})	The area under the plasma concentration versus time curve during a 1 week period at steady-state (AUC during the wear period for Week 5),
C _{max,ss}	The maximum observed plasma concentration over a dosage interval at
	steady-state (Week 5)
T _{max,ss}	Time to reach $C_{max,ss}$. If the maximum value occurs at more than one time point, $T_{max,ss}$ is defined as the first time point with this value.
C _{min,ss}	Minimum observed non-zero plasma concentration over a dosage interval at steady state (Week 5)
T _{min,ss}	The time to reach C _{min,ss} at steady-state (Week 5)
Cavg,ss	The average plasma concentration over the dosing interval at steady- state (Week 5), calculated as: $C_{avg,ss}=AUC_{tau}/tau$, with $AUC_{tau}=AUC_{0-168,SS}$ and tau = 168 h
FLUCP _{ss}	Percent peak-to-trough fluctuation within the 168 h wear period at steady-state on Week 5, calculated as:
	FLUCP=(C _{max,ss} -C _{min,ss})/C _{avg} x 100, where C _{min,ss} and C _{max,ss} are obtained between 0 and tau (168 h)
Ctrough,ss	The plasma concentration at the end if the steady-state dosing interval (Day 35)
C _{tau}	The plasma concentration at the end of each dosing interval, taken on Days 8, 15, 22, 29, and 35

Page 19 of 61 Confidential

The following PK parameters will be calculated for Week 5 for donepezil and 6-O-desmethyl donepezil for orally-administered Aricept:

Parameter	Description
AUC _{0-24,ss} (AUC _{tau})	The area under the plasma concentration versus time curve at steady-state, from time zero to 24 h after Day 35 administration, calculated by the linear trapezoidal rule.
AUC _{0-168,ss}	The area under the plasma concentration versus time curve at steady-state; this will be estimated by multiplying $AUC_{0-24,ss}$ on Day 35 by 7.
C _{max,ss}	The maximum observed plasma concentration at steady-state on Day 35
T _{max,ss}	The time to reach C _{max,ss} on Day 35
C _{min,ss}	Minimum observed non-zero plasma concentration over a dosage interval at steady state (Day 35)
T _{min,ss}	The to reach C _{min,ss} at steady-state (Day 35)
C _{avg,ss}	The average plasma concentration at steady-state on Day 35, calculated as: $C_{avg,ss}$ =AUC _{tau} / _{tau} , with tau = 24 h
FLUCPss	Percent peak-to-trough fluctuation on Day 35, calculated as:
	FLUCP=(C _{max,ss} -C _{min,ss})/C _{avg,ss} x 100, where C _{min,ss} and C _{max,ss} are obtained between 0 and tau (24 h)
Ctrough,ss	The plasma concentration at the end if the steady-state dosing interval (Day 36)
C _{tau}	The plasma concentration at the end of each dosing interval, taken on Days 8, 15, 22, 29, and 36

6.3 Conventions

All safety and clinical data listings, summaries, figures and statistical analyses will be generated using SAS (Version 9.4 or higher)².

Page 20 of 61 Confidential

Summaries of the clinical data will be presented by treatment/sequence and/or overall as depicted in the TFL shells.

PK data listings, summaries, figures, and statistical analyses will be generated using PhoenixTM WinNonlin[®] (Version 8.1 or higher) or SAS (Version 9.4 or higher). PK concentration data and PK parameter data will be summarized by analyte and treatment at each nominal sample time.

Treatment labels will be displayed as follows:

Treatment A Treatment B Treatment C

A: 5 mg/day TDS applied weekly, 7-day wear B: 10 mg/day TDS applied weekly, 7-day wear C: 10 mg oral Aricept® tablets, QD for 35 days

Treatment sequence labels will be displayed as follows:

Sequence ABC Sequence ACB

Listings will be sorted in the following order treatment sequence (ABC then ACB), subject, treatment, parameter (where applicable), and visit/timepoint (where applicable) unless otherwise stated.

For safety and clinical data continuous variables will be summarized by the number of nonmissing observations, mean, median, standard deviation, and minimum and maximum. Categorical variables will be summarized by presenting the frequency and percent. Percentages will be based on the number of non-missing observations or the subject population unless otherwise specified. For each variable, all categories will be shown. Zero frequencies (but not the percent) within a category will be presented.

PK data (concentration-time data and PK parameter data) will be summarized by the number of non-missing observations (n), arithmetic mean (mean), standard deviation (SD), median, minimum (min), maximum (max), and coefficient of variation (CV%), geometric mean, geometric CV%, Q1 (25th percentile), and Q3 (75th percentile). The geometric CV% will be calculated as 100*sqrt[exp(σ^2)-1], where σ^2 was the variance of the log-transformed data. Summaries for PK parameters T_{lag} and $T_{max,ss}$ will not include the geometric mean or geometric CV%.

Page 21 of 61 Confidential

6.3.1 Decimal Places

Non-PK Data

Decimal places for derived data described in section 6.2 will be determined by the scale of measurement unless otherwise stated. No decimal places will be displayed if the smallest calculated value is \geq 100; 1 decimal place will be displayed when the smallest value is within the interval (10, 100), with 10 being inclusive; 2 decimal places will be displayed when the smallest value is within (1, 10), with 1 being inclusive; and so on for even smaller scales of measurement.

Derived data where it is known in advance the result will be an integer for example day, month, year, number of days and total scores (for rating scales) will be presented with zero decimal places.

Means, medians and percentiles will be displayed to one more decimal place than the data, dispersion statistics (e.g. standard deviation) will have two more decimal places, and the minimum and maximum will be displayed to the same number of decimal places as reported in the raw data. Percentages will be displayed with one decimal place.

PK Data

Individual donepezil and 6-O-desmethyl donepezil concentrations, PK parameters, and summary statistics will be presented to the precision described in the table below. Time will be presented to 2 decimal places in tables and listings.

WORLDWIDE CLINICAL TRIALS SCIENTIFICALLY MINDED • MEDICALLY DRIVEN Corium, Inc. CL-P-20003 Statistical Analysis Plan Version 2.0 Issue Date 15-JUL-2021

Parameter	Individual Values (Table/Listing)	Arithmetic Mean, Geo Mean (Table)	SD (Table)	CV%, Geo CV% (Table)	Median, Max, Min, Q1, Q3 (Table)
Donepezil or 6-O-desmethyl donepezil concentrations	3 sf	2 dp	3 dp	1 dp	3 sf
Time-based parameters (T_{max} , T_{lag} , $T_{max,ss}$, $T_{min,ss}$) ^a	2 dp	3 dp	4 dp	1 dp	2 dp
$C_{max}, C_{max,ss}, C_{min,ss}, C_{avg,ss}, C_{trough,ss}, C_{tau}$	3 sf	2 dp	3 dp	1 dp	3 sf
AUC parameters (AUC ₀₋₂₄ , AUC ₀₋₁₆₈ , AUC _{0-168,ss} AUC _{0-24,ss})	2 dp	3 dp	4 dp	1 dp	2 dp
FLUCP _{ss}	3 sf	2 dp	3 dp	1 dp	3 sf

Note: sf=significant figure, dp=decimal place.

^aSummaries for PK parameters $T_{max,ss}$ and $T_{min,ss}$ will not include the geometric mean or geometric CV%.

Number of subjects (n) will be reported as a whole number. Percent ratios of the geometric least squares means and associated 90% confidence intervals will be reported to 2 decimal places, p-values will be reported to 4 decimal places.

6.4 Subject Disposition

Subject and patch disposition data will be summarized as follows:

- Subject level summaries will include:
 - The number of subjects screened
 - The number of subjects who are in each analysis population will be summarized by treatment sequence and overall for the Randomized Population.
 - The number of subjects who completed the study by treatment sequence for the Randomized Population
 - The number of early terminations, the primary reason for termination will be tabulated by treatment (last treatment received prior to discontinuing from the study) and overall for the Randomized Population.
- Patch level summaries will include:

Page 23 of 61 Confidential

- The number of patches applied for each treatment
- The number of patches in each population (i.e. Adhesion Population and Skin Irritation Population) by treatment
- The number of patches excluded and the reason for exclusion from each TDSbased population

All subject and patch level disposition data will be listed separately.

6.5 **Protocol Deviations**

A summary (number, %) of all major and minor protocol deviations will be provided by category reported overall for all subjects. Additionally, a listing of all protocol deviations will be provided within Appendix 16.2.

6.6 Baseline Comparability

Demographics and baseline characteristics will be assessed by treatment sequence and overall in a descriptive manner using the Safety and PK populations, but no formal statistical testing will be performed.

Standard continuous (n, mean, median, SD, Q1 (25th percentile), Q3 (75th percentile) and minimum and maximum values) or categorical variable (number, %) summaries will be presented for the following:

- Demographic data
 - Age at informed consent (IC)
 - Sex M/F
 - Race (White, Black or African American, Asian, American Indian or Alaska Native, Native Hawaiian or Other Pacific Islander, Mixed Race)
 - Ethnicity (Hispanic or Latino, Not Hispanic or Latino)
- Baseline characteristics
 - Height at Screening (cm)
 - Weight at Screening (kg)
 - Body Mass Index (BMI) at Screening (kg/m²)
 - o Skin type

Individual subject listings of all demographic, medical history, COVID-19 data and baseline characteristics data will be provided.

Page 24 of 61 Confidential

6.7 Medical History

A complete listing of subject medical history including previous/ongoing conditions and relevant surgical procedures will be presented for the Safety Population.

Medical history data will be coded using the Medical Dictionary of Regulated Activities (MedDRA version 23.1) primary system organ class (SOC) and preferred term (PT).

6.8 Prior and Concomitant Medications

Medications will be coded using the World Health Organization Drug Dictionary Enhanced (WHODDE), version September 2020. Medications entered on the eCRF will be mapped to Anatomic Therapeutic Chemical (ATC) drug class (level 3) and drug name. If ATC drug class level 3 is not available, then ATC drug class level 2 will be utilized. If ATC drug class levels 3 and 2 are not available, then ATC drug class level 1 will be utilized.

The study phase during which each medication was received (e.g., prior, concomitant, or both) will be presented in a subject data listing. The study phase of each medication, determined programmatically based on medication start and end dates, will be presented in the listing. A prior medication is defined as any medication administered prior to the date of the first dose of study drug. A concomitant medication is defined as any medication may be defined as both prior and concomitant. If it cannot be determined whether a medication was received prior to the start of study drug dosing due to partial or missing medication start and/or end dates, it will be considered a prior medication. Likewise, if it cannot be determined whether a medication was received after the start of study drug dosing, it will be considered concomitant.

For concomitant medications, the number and percentage of subjects receiving any medication will be summarized as will the number and percentage receiving any medication by ATC drug class and generic drug name. Subjects reporting use of more than one medication at each level of summarization (any medication received, ATC class, and generic drug name) will be counted only once. ATC class terms will be displayed by descending order of incidence, as will generic drug names within each ATC class.

6.9 TDS Application Data

All TDS application and removal data will be listed.

6.10 Statistical Analysis of PK Data

Page 25 of 61 Confidential

The Relative Bioavailability population will be used in the statistical analyses.

6.10.1 Statistical PK Comparison between Treatments

Statistical comparison of the PK parameters of donepezil and 6-O-desmethyl donepezil exposure ($AUC_{0.24,ss}$, $AUC_{0-168,ss}$, $C_{max,ss}$, $C_{min,ss}$, $C_{tau,ss}$, $C_{avg,ss}$, and FLUCP,ss) at steady-state will be performed using an Analysis of Variance (ANOVA) model for a 2-way crossover design for the comparison of 10 mg TDS vs. Aricept (Treatment B vs. Treatment C) on the ln-transformed data with sequence, period and treatment as the fixed effects and subject within sequence as a random effect. For comparison of 5 mg/day TDS vs. Aricept (Treatment A vs. Treatment C) the analysis will be performed using a ANOVA model with treatment as fixed effect and subject as random effect with Treatment A being dose normalized (PK parameter values multiplied by 2) before the analysis. A statistically significant difference is defined as p <0.05.

Geometric means. inter-subject and intra-subject variability (coefficient of variation in percent, CV_{intra} % and CV_{inter} %, respectively), and intraclass correlation (Chow and Liu, 2009)⁴ of the PK parameters will be calculated based on the mixed model results (Proc Mixed of SAS) as indicated below:

Page 90

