STATISTICAL ANALYSES	PharmacokineticsPlasma concentrations and PK parameters of donepezil and 6-O-desmethyl donepezil will be tabulated using summarystatistics.To examine the donepezil PK at steady state (Week 5 of 5 x1-week wear) after 5 and 10 mg/day TDS applicationcompared to oral Aricept ® , an analysis of variance (ANOVA)will be performed on the natural logarithms of AUC0-168,SSand C max . Dose-normalization will be applied as appropriate.Differences between each Test and Reference in the PKparameters will be tested at the 5% level of significance.
	Time to Steady State Assessment Assessment of time to achieve steady-state will be performed by a review of weekly donepezil trough levels (C tau ) at time points immediately prior to dosing on Days 15, 22, 29, and 36 in each treatment period. The univariate analysis method described by Chow and Liu for examining when steady-state is attained will be implemented using log-transformed trough plasma concentrations. Modifications to the method for Treatment Periods 2 and 3 will be explained in the Statistical Analysis Plan (SAP), to possibly adjust for the attainment of a new steady state after switching to a new treatment without a washout period after the previous treatment.
	Relative BioavailabilityTo examine the relative bioavailability at steady state of the5 and 10 mg/day TDS (Tests) relative to oral donepezil(Reference), plasma donepezil exposure as characterized byAUC 0-168 at steady state will be assessed and comparedutilizing bioequivalence criteria.Since the intention of the patch is to decrease the peak-to-

through fluctuations with lower $C_{max}$ after the patch application compared to daily oral Aricept dosing, rather than using the conventional bioequivalence criterion for $C_{max}$ , it is stipulated that mean steady-state donepezil $C_{max}$ after patch administration should remain between the steady-state $C_{max}$ and $C_{min}$ after daily oral Aricept ® administration.

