# **17.3.2.** Descriptive Statistics for Pharmacokinetics

For the plasma concentrations at each time point and for each PK parameter, parametric and nonparametric descriptive statistics will be calculated. Parametric descriptive statistics include number of subjects (n), arithmetic mean and standard deviation (SD), and percent coefficient of variation (%CV). Nonparametric descriptive statistics include minimum, Q1 (25th percentile), median, Q3 (75th percentile), and maximum. Individual plasma concentrations and PK parameters and descriptive statistics by treatment will be listed.

PK parameters of exposure (concentrations and AUCs) after the 5 mg/day TDS application will be multiplied by 2 to adjust for the lower dose (dose-normalization) before comparison to the 10 mg/day treatments.

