# 17.3.4. Statistical PK Comparison between Treatments

Statistical comparison of the PK parameters of exposure (AUC0-24,SS, AUC0-168,SS, Cmax, Cmin, Ctau, percent peak-to-trough fluctuation (FLUCP).) at steady state for donepezil among the 3 treatments will be performed using an Analysis of Variance (ANOVA) model for a 3-way crossover design on the ln-transformed data with sequence, period and treatment as the fixed effects and subject within sequence as a random effect. A statistically significant difference is defined as p <0.05. Intersubject, intrasubject and total variability (coefficient of variation in percent, CV%) of the PK parameters will be reported.

PK parameters of exposure (concentrations and AUCs) after the 5 mg/day TDS application will be multiplied by 2 to adjust for the lower dose (dose-normalization) before statistical comparison to the 10 mg/day treatments.

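### SAP 6.10.1, followed as written, doubles the 5 mg patch's percent fluctuation (FLUCP,ss) before comparing it with Aricept, although FLUCP does not scale with dose

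*SAP*

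**What the plan says.** SAP 6.10.1 has a single list of parameters for the between-treatment comparison: AUC0-24,ss, AUC0-168,ss, Cmax,ss, Cmin,ss, Ctau,ss, Cavg,ss "and FLUCP,ss) at steady-state will be performed using an Analysis of Variance (ANOVA) model". It covers donepezil and its metabolite. The 5 mg patch (Treatment A) versus Aricept (Treatment C) analysis is then to be done "with Treatment A being dose normalized (PK parameter values multiplied by 2) before the analysis". No parameter is exempted. The same paragraph adds the decision rule, "A statistically significant difference is defined as p <0.05", and the next one takes further output from the same models: "Geometric means. inter-subject and intra-subject variability (coefficient of variation in percent".

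SAP 6.2.11.2 defines FLUCP,ss as (Cmax,ss − Cmin,ss)/Cavg × 100, over 168 h for the patches and 24 h for Aricept. Addendum section 2.1.2 gives the same formula.

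The protocol is narrower about the factor. Section 17.3.2 says "PK parameters of exposure (concentrations and AUCs) after the 5 mg/day TDS application will be multiplied by 2 to adjust for the lower dose", and 17.3.4 repeats the restriction for the statistical comparison: "PK parameters of exposure (concentrations and AUCs) after the 5 mg/day TDS application will be multiplied by 2". The synopsis says "Dose-normalization will be applied as appropriate". SAP section 7 reports no changes to the protocol's planned analysis.

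**The concern.** Dose normalization is meant to put 5 mg values on a 10 mg footing. That makes sense for a parameter proportional to dose. FLUCP is a ratio of concentrations and is not proportional to dose, so multiplying it by 2 corrects nothing and introduces a bias.

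FLUCP is a secondary endpoint (SAP 3.2). It appears in no stated objective and no bioequivalence rule depends on it. However, protocol 17.3.6 says the patch is intended to reduce peak-to-trough fluctuation relative to daily tablets, and FLUCP is the parameter that measures this directly. Addendum section 2.3 removed from the SAP the criterion placing patch Cmax between oral Cmax and Cmin, so FLUCP is the SAP's remaining direct comparison on that property. The error would run against the product: a true reduction of up to 50% would look like no change or an increase.

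**Working it through.** The plan states no FLUCP figure to reproduce, so the check is algebra followed by an illustration of size.

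**1. FLUCP does not depend on dose.** If every concentration is multiplied by 2,

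(2·Cmax − 2·Cmin)/(2·Cavg) × 100 = (Cmax − Cmin)/Cavg × 100.

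To illustrate, take an assumed profile of 20, 24, 28, 30, 27, 23, 20 at 0, 24, 48, 84, 120, 144, 168 h. The linear trapezoidal AUC is 4338, so Cavg = 4338/168 = 25.82 and FLUCP = (30 − 20)/25.82 × 100 = 38.73%. Recomputed from doubled concentrations it is still 38.73%. Doubling FLUCP itself gives 77.46%.

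**2. Effect on the comparison.** On ln-transformed data, doubling adds ln 2 = 0.693 to every Treatment A value. The A/C geometric mean ratio r is therefore reported as 2r: 0.50 becomes 1.00, 0.60 becomes 1.20, 1.00 becomes 2.00. This holds whatever the variability. Variance estimates do not change, because a constant factor only shifts the log mean.

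**3. Effect on the p-value.** Inputs:
- 48 completers (SAP section 4), each contributing one A and one C value, giving 47 df and t(0.975) = 2.012.
- The intra-subject CV of FLUCP is not given in the documents; 20% to 60% is assumed.
- The estimate is taken to equal the true ratio.

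Formulas:
- SE = √[2·ln(1 + CV²)/48]
- The correct analysis shows a significant reduction when r < exp(−t·SE).
- The analysis as written shows a significant increase when r > 0.5·exp(t·SE).
- Between those two limits, a significant reduction is reported as a significant increase.
- The analysis as written is non-significant for r from 0.5·exp(−t·SE) to 0.5·exp(t·SE).

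| Assumed CV | SE | 0.693/SE | Reduction reported as increase, r | Reported as non-significant, r |
|---|---|---|---|---|
| 20% | 0.0404 | 17.1 | 0.542–0.922 | 0.461–0.542 |
| 40% | 0.0786 | 8.8 | 0.586–0.854 | 0.427–0.586 |
| 60% | 0.1132 | 6.1 | 0.628–0.796 | 0.398–0.628 |

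Worked case at CV 60%:
- Correct: r = 0.75, ln 0.75 = −0.288, t = −0.288/0.1132 = −2.54, p = 0.014.
- As written: 2r = 1.50, ln 1.50 = 0.405, t = 0.405/0.1132 = 3.58, p = 0.0008.

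Across the whole assumed CV range, a true ratio of 1.00 is reported as 2.00 with p < 0.0001, and a true ratio of 0.50 as 1.00 with p = 1.

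**The case against.** The best defence is that the sentence should be read in context. The A versus C sentence repeats neither the parameter list nor the log transformation; both come from the sentence before it. If context supplies those, it can also supply the protocol's restriction, because the SAP says it is based on the protocol and declares no change. On that view the operative instruction is to dose-normalize, and properly normalizing FLUCP leaves it alone. A programmer could also recompute FLUCP from the dose-normalized concentrations listed for Tables 14.4.7 to 14.4.10, and no error would arise.

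This stands as far as it goes: the documents do not show that FLUCP was doubled. But it relies on someone departing from the only rule the SAP states. The protocol is not perfectly clean either. Section 17.3.4 lists FLUCP among its exposure parameters ("percent peak-to-trough fluctuation (FLUCP).) at steady state for donepezil among the 3 treatments will be performed"), although the bracket in its scaling sentence still leaves FLUCP out.

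Three further limits are fair:
- It is uncertain where a wrong value would surface. SAP 6.10.3 names only AUC0-168,ss and Cmax,ss for ratios and intervals, so a FLUCP ratio may never be tabulated. A FLUCP p-value could still appear in the treatment-comparison output (Listing 16.2.6.4), whose contents are not shown.
- Part of 6.10.1 after the sentence introducing the variability formulas is not visible in the public text. It could bear on this, though the visible rule is complete as it stands.
- The reversal ranges rest on assumed CVs. Only the factor of 2 comes from the documents.

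**Conclusion.** The concern holds. The instruction in SAP 6.10.1, applied as written, gives a wrong value for a secondary endpoint and is broader than the protocol's rule. The bias is exactly 2-fold in the A/C FLUCP ratio, with no assumption beyond the plan's own definition of FLUCP. How often that changes a significance statement depends on the assumed CV of 20% to 60% and on 48 pairs. Under those assumptions, reductions of roughly 20% to 37% (CV 60%) or 8% to 46% (CV 20%) would be reported as significant increases.

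Affected, if the rule is followed literally: the Treatment A geometric mean of FLUCP from the A versus C model, the A versus C p-value, and any ratio or interval tabulated from it, for donepezil and the metabolite. Not affected: the AUC and Cmax comparisons, the primary 10 mg versus Aricept comparison, the CV estimates and the sample size. This is a rule that should be corrected, not a demonstrated error in results.

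**What to change.** In SAP 6.10.1, state that the factor of 2 applies only to AUC0-24,ss, AUC0-168,ss, Cmax,ss, Cmin,ss, Ctau,ss and Cavg,ss, and that FLUCP,ss is compared unscaled, as protocol 17.3.2 and 17.3.4 imply. Then check the A versus C FLUCP output. If FLUCP is shown in Table 14.4.16 (dose-normalized Week 5 parameters), it should equal the 5 mg value in Table 14.4.12.

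The cost is one sentence in a further controlled addendum (the existing one is already post database lock) and that check. A re-run of the A versus C FLUCP output and Table 14.4.16 is needed only if FLUCP was doubled. No new data are needed and the primary analysis does not change.

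A separate query on the same section, not an established error: confirm whether the variance terms in the addendum's intraclass correlation formula (section 2.2.2) are mean squares, for which it is correct with two observations per subject, or variance components, for which it returns 2·ICC − 1.
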